#### 2.5.4 Supportive analyses

Sensitivity analyses and supplementary analyses will be conducted in order to provide evidence that the results seen from the primary analysis are robust.

Sensitivity analyses will be conducted to determine the impact of missing data handling on the primary estimand.

- Tipping point analysis
- In case an imbalance in the distribution of any baseline demographics and disease characteristics impacting response (e.g., gender and smoking status) is seen, additional analyses may be performed adjusting for these variables in the model
- The unused models described in [Section 2.5.3](#) may be used for sensitivity analysis, if appropriate (e.g., if they converge).

Additional supplementary analyses may be conducted to examine different estimands which are also deemed clinically relevant, such as the estimand based on the hypothetical strategy which would examine the treatment effect in outcomes where biologic rescue was not available to subjects.

The effect of the COVID-19 pandemic on the study will be monitored and assessed. Additional supplementary analyses to study the potential effect of the pandemic on the primary estimands may be performed, and are described in [Section 2.15](#).

## 2.6 Analysis of secondary efficacy objectives

### 2.6.1 Secondary endpoints

The secondary efficacy variables are listed below.

1. Change from baseline in mSASSS at Week 104
2. No new syndesmophyte at Week 104
3. Change from baseline in ASspiMRI-a Berlin modification score at Week 104
4. Change from baseline in Berlin SI joint edema score at Week 104
5. ASAS20 at Week 104
6. ASAS40 at Week 104
7. ASAS partial remission at Week 104
8. ASDAS inactive disease at Week 104

## 2.6.2 Statistical hypothesis, model, and method of analysis

**The secondary efficacy variables and the method for adjusting for multiplicity are described below. All analysis will be based on the FAS population unless otherwise specified. Modified Stoke Ankylosing Spondylitis Spine Score (mSASSS) at Week 104**

Change from baseline in mSASSS will be evaluated using ANCOVA model with treatment as a factor and baseline mSASSS as a covariate.

Estimand definition:

- Population – defined through appropriate inclusion/exclusion criteria to reflect the targeted AS population
- Variable – mSASSS change from baseline at Week 104
- Intercurrent event – regardless of adherence to randomized treatment
- Summary measure – difference in means

### **Absence of new syndesmophytes at Week 104**

The proportion of subjects with no new syndesmophyte will be evaluated using a logistic regression model with treatment group as a factor and baseline mSASSS as a covariate.

Difference in marginal response proportions with p-value and respective 95% confidence interval will be estimated from the logistic regression model.

Estimand definition:

- Population – defined through subjects with syndesmophyte at baseline, within the targeted AS population defined by the inclusion/exclusion criteria
- Variable – binary response variable indicating absence of new syndesmophyte at Week 104. Absence of new syndesmophyte is defined as having individual vertebral scores < 2 for each interpretable location which had no syndesmophyte at baseline.
- Intercurrent event – regardless of adherence to randomized treatment
- Population-level summary – difference in proportion of absence of new syndesmophyte between the secukinumab and GP2017 arms

### **MRI of spine and SI joints**

MRI analysis will be based on a subgroup of subjects who have MRI performed on spine and SI joints at selected sites.

The change from baseline to Week 104 in ASspiMRI-a Berlin modification score and Berlin SI joint edema score will be evaluated using a non-parametric ANCOVA model with treatment as a factor and baseline score as a covariate. Pairwise comparison will be performed for secukinumab (150 mg s.c. or 300 mg s.c.) versus GP2017. These will be assessed and analyzed outside of the testing strategy.

If values are missing for the baseline or post-baseline visit, the subject will be excluded from the analysis.

Summary statistics of observed data by visit and change from baseline will be provided for each treatment regimen. Summary statistics include mean, standard deviation, minimum, lower quartile, median, upper quartile and maximum.

### **ASAS 20, ASAS 40, ASAS partial remission and ASDAS inactive disease at Week 104**

Response at Week 104 to ASAS 20, ASAS 40, ASAS partial remission and ASDAS inactive disease will be evaluated using a logistic regression model with treatment group as a factor and baseline score (if appropriate) as a covariate. These will be assessed and analyzed outside of the testing strategy.

#### **Testing strategy**

The following hypotheses will be included in the testing strategy, which controls the family-wise two-sided type I error at 5% level. The two primary hypotheses (H1 and H2) form the first family, which will be tested first at 5% level using the [Hochberg \(1988\)](#) procedure. The second family consists of the secondary hypotheses (H3 through H6), which will be tested only if both primary hypotheses have been rejected, and will be tested at 5% level using the graphical approach for sequentially rejective procedures ([Bretz 2009](#)) as illustrated in [Figure 2-1](#).

#### **Primary hypotheses:**

H1: secukinumab 150 mg is not different from GP2017 40 mg with respect to proportion of subjects with no radiographic progression at Week 104

H2: secukinumab 300 mg is not different from GP2017 40 mg with respect to proportion of subjects with no radiographic progression at Week 104

#### **Secondary hypotheses:**

[figure not shown]
H3: secukinumab 150 mg is not different from GP2017 40 mg with respect to change from baseline in modified Stoke Ankylosing Spondylitis Spine Score (mSASSS) at Week 104

H4: secukinumab 300 mg is not different from GP2017 40 mg with respect to change from baseline in modified Stoke Ankylosing Spondylitis Spine Score (mSASSS) at Week 104

H5: secukinumab 150 mg is not different from GP2017 40 mg with respect to proportion of subjects with a syndesmophyte at baseline with no new syndesmophytes at Week 104

H6: secukinumab 300 mg is not different from GP2017 40 mg with respect to proportion of subjects with a syndesmophyte at baseline with no new syndesmophytes at Week 104

**Figure 2-1 Testing strategy for the second family after both H1 and H2 have been rejected**

The family-wise error rate will be controlled strongly at  $\alpha=5\%$  two-sided level with the proposed hierarchical testing strategy. In the first family, the Hochberg procedure will reject H1 and H2, if both of them are significant at level  $\alpha$  simultaneously. Otherwise, it will reject H1 if it is significant at level  $\alpha/2$ , or reject H2 if it is significant at level  $\alpha/2$ . Because H1 and H2 represent two doses of secukinumab versus GP2017, the correlation between the two test statistics will be positive. In this case, the type I error is controlled for the Simes test (Sarkar and Chang 1997) and, thus, the family-wise error rate is controlled strongly for the Hochberg procedure. Once both primary hypotheses within the first family are rejected, then the  $\alpha$  will be passed to the second family starting with each of the hypotheses H3 and H4 tested simultaneously at  $\alpha/2$ . Then based on the rejection of one or both of these hypotheses (H3 and H4), the next endpoint will be tested hierarchically for each dose (through H5 and/or H6), respectively. This procedure will continue (pending rejection of the null hypotheses) until H5 and/or H6 are/is rejected respectively; then the respective  $\alpha/2$  can be passed on to the other secukinumab regimen’s hierarchy of hypotheses in the second family (i.e., H3 or H4), if they are not already rejected at  $\alpha/2$ . Of note, in the description above, rejection of a hypothesis refers to rejection of the two-sided hypothesis; however, the level of a rejected hypothesis is only passed on according to the graphical procedure for the test of another hypothesis if the treatment effect is in favor of secukinumab.

### 2.6.3 Handling of missing values/censoring/discontinuations

Missing Week 104 change from baseline values in mSASSS for a given subject will be imputed using an imputation model based on the observed data of subjects in the same randomized arm who also discontinued study treatment but for whom Week 104 X-ray data are available (‘retrieved dropout approach’, EMA 2010). Recent literature suggests that in AS patients treated with TNF inhibitors, the spinal radiographic progression followed a linear course during the first 4 years of follow-up (Maas, et. al. 2017). Therefore, a parametric model assuming a normal distribution and a linear time trend for the mean scores will be used to impute missing Week 104 values. The model will be fitted to the average of the three readers’ change from baseline in mSASSS.

We will consider a mixed-effects model for the change in mSASSS functional scale measurement. Let  $y_{ij}$  be the  $j^{\text{th}}$  change from baseline measurement of subject  $i$ , at time  $t_{ij}$ :

$$y_{ij} = \alpha_i t_{ij} + \epsilon_{ij} \text{ with } \epsilon_{ij} \sim N(0, \sigma^2).$$

The subject specific intercept  $\alpha_i$  will be modelled using treatment and the subject's baseline mSASSS value as fixed effects and assuming a subject-specific normally distributed random effect.

PROC MCMC will be used for fitting the mixed-effects model and multiple imputation of the Week 104 value, with weakly informative priors and model code as shown below,

```
random gamma ~ normal(0, sd=sd_re) subject=usubjid;
prior beta1 ~ normal(0,sd=100);
prior beta2 ~ normal(0,sd=100);
prior beta3 ~ normal(0,sd=100);
prior beta4 ~ normal(0,sd=100);
prior beta5 ~ normal(0,sd=100);
prior sd_re ~ uniform(0,20);
prior sd ~ uniform(0,20);
mu = (beta1*trt_GP2017 + beta2*trt_SEC150 + beta3*trt_SEC300 + beta4*base +
beta5*sq_base_stand + gamma)*ady/365.25;
model chg ~ normal(mu, sd=sd);
```

where trt\_GP2017 – binary indicator for GP2017 40 mg

trt\_SEC150 – binary indicator for secukinumab 150 mg

trt\_SEC300 – binary indicator for secukinumab 300 mg

base – baseline mSASSS

sq\_base\_stand – square root of baseline mSASSS (standardized)

gamma – random effect

ady – number of days when X-ray assessment was done after randomization

chg – change from baseline in mSASSS at Week 104

For absence of new syndesmophytes at Week 104, the handling of missing data will be the same as the primary endpoint.

For MRI endpoints, if values are missing for the baseline or post-baseline visit, the subject will be excluded from the analysis.

Multiple imputation (MI) approach under missing-at-random (MAR) assumptions will be applied to handle missing data for ASAS20, ASAS40, ASAS partial remission and ASDAS inactive disease.

[figure not shown]

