3.1 Study design

This multicenter study uses a randomized, partially-blinded, active-controlled, parallel-group design in subjects with AS. A screening period (SCR) of up to 10 weeks before randomization will be used to assess eligibility followed by 104 weeks of treatment. Two follow-up visits at Weeks 112 and 120 will occur thereafter.

At baseline (BSL), approximately 837 subjects whose eligibility is confirmed will be randomized to one of three treatment groups (1:1:1).

- Group 1: secukinumab 150 mg [1 x 1.0 mL s.c. plus placebo (1 x 1.0 mL s.c.)] at BSL, Weeks 1, 2 and 3, followed by administration every four weeks starting at Week 4
- Group 2: secukinumab 300 mg (2 x 1.0 mL s.c.) at BSL, Weeks 1, 2 and 3, followed by administration every four weeks starting at Week 4
- Group 3: GP2017 (adalimumab biosimilar) 40 mg (1 x 0.8 mL s.c.) at BSL followed by administration every two weeks

[figure not shown]
Although study treatment (secukinumab vs GP2017) will be provided in an open-label fashion to the subjects, secukinumab study treatment will be blinded to the dose. Subjects in groups 1 and 2 will know that they are on secukinumab, but will be blinded to which treatment arm and will not know whether they are receiving secukinumab 150 mg or 300 mg. Subjects in the GP2017 treatment group will know that they are receiving GP2017 (adalimumab biosimilar) 40 mg. Sponsor blinding is described in [Section 5.4](#).

Although no subject will be restricted from receiving necessary rescue medications for lack of benefit or worsening of disease, if rescue treatment with prohibited medications (as described in [Section 5.5.8](#)) occurs, subjects may remain in the study but must discontinue study treatment. All subjects may remain in the study and should continue study-related assessments up to completion, regardless of whether they continue study treatment or not. Subjects who are deemed not to be benefiting from the study treatment based upon safety and efficacy assessments by the investigator or for any reason on their own accord will be free to discontinue study treatment only or any further participation in the study at any time.

[REDACTED]

Two follow-up visits are to be completed after last administration of study treatment for all subjects, regardless of whether they complete the entire study as planned or discontinue prematurely.

Figure 3-1 Study design

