
S To be recorded in source document but not in CRF
 
Greyed visits are visits with at-home dosing, optional for on-site dosing
 
The BSL visit and randomization is Day 1
 
1 Eligibility and relevant medical history assessments are conducted at SV1, SV2 and BSL.
 
2 SI joint and spinal X-ray image acquisition must follow the vendor's Image Acquisition Guidelines. An SI joint X-ray taken within 3 months prior to SV1 may be utilized. The SI joint X-ray will be centrally read for eligibility.
 
3 Spinal X-rays (cervical + thoraco-lumbar) to be collected during the screening period to confirm eligibility for subjects with CRP < 5 mg/L. Subjects with CRP ≥ 5 mg/L and confirmed study eligibility should obtain the spinal X-rays at BSL.
 
4 Re-screening subjects may utilize previous X-rays if taken within the past 3 months according to the imaging criteria.
 
5 The PPD skin test can be performed at any time during the screening period, but it must be read within 72 hours and before randomization.
 
6 AS disease assessment includes: AS disease background, Modified New York criteria for AS and targeted medical history events related to AS.
 
7 A chest X-ray or MRI is required if it was not performed and evaluated within 3 months prior to screening. The X-ray should be performed after it is certain the subject meets inclusion/exclusion criteria in order to minimize unnecessary exposure to radiation. The X-ray may be replaced by an MRI assessment.
 
9 Sample must be obtained fasting.
 
10 MRI only performed in a sub-population of subjects at selected sites. All subjects at the selected MRI site should be considered for the MRI assessment.
 
11 AEs / SAEs occurring after the subject has signed the informed consent must be captured on the appropriate CRF.
 
For all subjects who discontinue from the study, the investigator should ensure that the subject completes the end of treatment visit (Week 104 visit assessments) 4 weeks after last study treatment of secukinumab or 2 weeks after last study treatment of GP2017, and also returns for the final follow-up visits, F112 and F120. Every attempt should be made to obtain the scheduled X-ray and MRI images at the final visit, unless the last X-ray and/or MRI were taken within 12 weeks before discontinuation.
 
** Hepatitis B and/or hepatitis C and/or HIV serology testing to be performed at local site during screening period, only if required per local medical practice or local regulations prior to initiation of therapy. These assessments will be documented in source records only and will not be entered into the CRF.
																																

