### 2.5.3 Handling of missing values/censoring/discontinuations

Missing Week 104 data for a given subject who discontinued in the study will be imputed using an imputation model based on the observed data of subjects in the same randomized arm who also discontinued study treatment but for whom Week 104 X-ray data are available ('retrieved dropout approach', [EMA 2010](#)) and based on the observed data of the given subject.

A logistic regression model will be fitted to the Week 104 X-ray data for the retrieved dropout patients, while adjusting for treatment, baseline mSASSS and post-baseline slope in mSASSS.

The post-baseline slope is defined as the last available post-baseline change in mSASSS score divided by study day on which the X-ray was taken. Recent literature suggests that in AS patients treated with TNF inhibitors the spinal radiographic progression followed a linear course during the first 4 years of follow-up (Maas, et. al. 2017). Thus, the linearity assumption is expected to be reasonable. The covariates of baseline mSASSS and slope will be standardized to have a mean of 0 and standard deviation of 1 before model fitting.

PROC MCMC will be used for fitting the logistic regression model and multiple imputation of the Week 104 value, with weakly informative priors and model code as shown below,

```
prior beta1 ~ normal(0,sd=2);
```

```
prior beta2 ~ normal(0,sd=2);
```

```
prior beta3 ~ normal(0,sd=2);
```

```
prior beta4 ~ normal(0,sd=3);
```

```
prior beta5 ~ normal(0,sd=3);
```

```
pi = logistic(beta1*trt_GP2017 + beta2*trt_SEC150 + beta3*trt_SEC300 +  
beta4*sqrt(base_stand) + beta5*slope_stand);
```

```
model noprog ~ binary(p = pi);
```

where trt\_GP2017 – binary indicator for GP2017 40 mg

trt\_SEC150 – secukinumab 150 mg

trt\_SEC300 – secukinumab 300 mg

sqrt(base\_stand) – square root of the baseline mSASSS (standardized)

slope\_stand – the last available post-baseline change in mSASSS score divided by study day on which the X-ray was taken (standardized)

noprog – no radiographic progression at Week 104

If all post-baseline values are missing for a subject, the subject will be imputed based on a similar model as above but just based on treatment and baseline value as covariates (without the post-baseline slope variable). Subjects with a missing baseline will be excluded from the analysis.

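### The radiographic imputation models count time from randomization, although change in mSASSS accrues from a baseline spine film that some subjects have weeks earlier

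*SAP*

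**What the plan says.** **Imputation clock.** For change in mSASSS (H3/H4), SAP 2.6.3 fits a mixed model in which expected change is a subject-specific rate multiplied by time, with no intercept. Time is "ady – number of days when X-ray assessment was done after randomization". For the primary endpoint (H1/H2), SAP 2.5.3 uses a logistic imputation model with a standardized slope covariate: "The post-baseline slope is defined as the last available post-baseline change in mSASSS score divided by study day on which the X-ray was taken". SAP 2.6.3 applies the primary endpoint's handling to absence of new syndesmophytes (H5/H6). Both sections justify the form of the model by a linear course of radiographic progression.

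**Day 1.** The notes to Protocol Table 6-1 state: "The BSL visit and randomization is Day 1".

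**Baseline film.** Footnote 3 of the same table splits subjects by entry route: "Spinal X-rays (cervical + thoraco-lumbar) to be collected during the screening period to confirm eligibility for subjects with CRP < 5 mg/L", whereas "Subjects with CRP ≥ 5 mg/L and confirmed study eligibility should obtain the spinal X-rays at BSL". Footnote 4 adds: "Re-screening subjects may utilize previous X-rays if taken within the past 3 months according to the imaging criteria". Protocol 3.1 allows "A screening period (SCR) of up to 10 weeks before randomization". Inclusion criterion 7 (Protocol 4.1) places the screening film after the central hsCRP result.

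**Baseline window.** SAP Table 5-3 maps X-rays up to Day 30 to baseline. SAP Table 5-4 defines baseline for all data as the last measurement on or before Day 1.

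**The concern.** A line through zero is the right shape for change from baseline only if time zero is the date of the baseline film. Neither model uses that date. When the film precedes randomization, the observed change covers a longer interval than the model credits, so the subject appears to progress faster than they do.

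The misalignment is systematic, because it follows the entry route. Subjects entering with hsCRP below 5 mg/L must have at least one syndesmophyte (inclusion criterion 7). Film lead time is therefore linked to baseline structural damage, which is also represented in both imputation models through baseline mSASSS. Those subjects should also be over-represented in the syndesmophyte subset used for H5/H6. At stake is whether imputed values for confirmatory endpoints follow the assumption the plan gives for them.

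**Working it through.** **1. The plan's own figure.** Protocol 9.7 and SAP 3 give about 68% power for mSASSS change (difference 0.58, SD 2.5, 279 per arm, alpha 0.025). The standardized difference is 0.58 / (2.5 × √(2/279)) = 2.74. Subtracting the critical value 2.24 leaves 0.50, which gives 69.1% (68.9% with the noncentral t). The figure reproduces, and this point does not alter it.

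**2. Error for one affected subject.** Let the baseline film be L days before randomization and the later film t days after it. Assume linear progression, as the SAP does, and prediction at 728 days after randomization (Day 729).

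- Rate ratio, randomization clock over film clock: (t + L)/t.
- Ratio for the extrapolated Week 104 change: (728/t) ÷ ((728 + L)/(t + L)). It is smaller because the true Week 104 change also runs from the film.

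With a Week 52 film (t = 364):

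| Baseline film | Rate ratio | Week 104 ratio |
|---|---|---|
| 35 days before (illustrative) | 399/364 = 1.096 | 2 ÷ (763/399) = 1.046 |
| 70 days before (outer limit, first screening) | 434/364 = 1.192 | 2 ÷ (798/434) = 1.088 |
| 91 days before (about 3 months, re-screened) | 455/364 = 1.250 | 2 ÷ (819/455) = 1.111 |
| Day 30, if Table 5-3 applies (L = −29) | 335/364 = 0.920 | 2 ÷ (699/335) = 0.959 |

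**3. In mSASSS points.** Let m be the mean change over 728 days. With L = 70 and t = 364, the extrapolated change is 2 × 434 = 868 days' worth of progression, and the true change is 798 days' worth. The excess is 70 × m/728. For the plan's means this is 0.05 (m = 0.52) and 0.11 (m = 1.1).

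**4. Arm mean.** Assume 20% of outcomes are imputed (from the 80% completion assumption), all with a Week 52 film, and that a share f of subjects has a 70-day lead. The documents do not give f. The shift is 0.20 × f × (0.05 to 0.106):

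- f = 10%: 0.001 to 0.002
- f = 30%: 0.003 to 0.006
- f = 100%: 0.010 to 0.021

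**5. Treatment contrast, H3/H4.** A simplified random-slope model was simulated with each clock. It assumed a slope SD of 1 per year, residual SD 1, known variance components, no baseline covariate, and arm rates estimated from all observed subjects. Missingness was 20%/20% or 15%/25%, and the last film was at 85 or 364 days. Changing the clock moved the difference by about 0.002 to 0.003 at f = 30% and by 0.005 to 0.011 at f = 100%, against a planned 0.58.

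**6. Primary and syndesmophyte models.** Here the slope is one standardized covariate in a logistic regression and nothing is extrapolated, so the Week 104 ratios in step 2 do not carry over. A 70-day lead inflates a slope from a Week 52 film by 19% and one from a Week 104 film by 10% (798/728 = 1.096). The effect on imputed response was not calculated.

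**The case against.** The strongest reply is that the error is narrow and has no demonstrated consequence. Most of that stands.

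- **Scope.** A reader might infer that progression rates are wrong for every imputed subject. The documents do not support this. Subjects with CRP of 5 mg/L or more are to be filmed at the baseline visit, and in the primary model a subject with no post-baseline film is imputed without a slope.
- **Early leavers.** A reader might infer that they fare worst, since a film 85 days after randomization with a 70-day lead gives a rate ratio of 155/85 = 1.82 and a Week 104 ratio of 1.66. That requires an early exit film to be used. Table 5-3 has no X-ray window for Days 31 to 275, and the SAP does not say whether such a film counts as the last available. In the simulated mixed model, early films were shrunk towards the arm mean and moved the contrast no more than Week 52 films did.
- **Donors against recipients.** A mismatch between retrieved dropouts and the subjects imputed from them is plausible if donors' slopes come from Week 104 films. Protocol 9.4.3, however, names baseline and Week 52 as the subject's own data. If both groups use Week 52 films, a given lead inflates both slopes by the same factor.
- **Day 30 baselines.** These rest on Table 5-3 alone and conflict with Table 5-4, so they cannot be treated as settled.
- **Size of lead.** Seventy days is an outer limit for a first screening, because the film follows the hsCRP result and Section 6 of the protocol does not require the full screening window.
- **Balance and stress tests.** Entry route is fixed before randomization and should balance across arms. The continuous tipping-point steps of 1/3 point exceed the 0.05 to 0.11 points found here, and the binary version covers every allocation of missing responses.

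What the reply does not remove is the misalignment itself. Tipping-point analyses stress the estimate but do not correct it.

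**Conclusion.** The clock is wrong as written in both imputation models for subjects whose baseline film was not taken at randomization: CRP below 5 mg/L entrants and re-screened subjects who reuse a film. With a 70-day lead and a Week 52 film, the error is about 19% on the rate and 9% on the linearly extrapolated Week 104 change. It is error in a covariate, of unquantified effect, for H1/H2 and H5/H6.

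For H3/H4 the contrast moves by about 0.01 or less, given at most 20% to 25% imputed per arm, similar lead times across arms and the assumed variance components. A reader might infer a biased treatment comparison or an altered trial conclusion. Nothing in the documents or the calculations supports that. This is a small specification error worth correcting because the models should implement the linearity they rely on.

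**What to change.** 1. In SAP 2.5.3, define the slope as the change divided by the days between the baseline film and the later film.
2. In SAP 2.6.3, replace ady with days since the baseline film, and predict at each subject's own interval from baseline film to Week 104.
3. Reconcile the X-ray baseline window in Table 5-3 (up to Day 30) with the baseline rule in Table 5-4 (on or before Day 1).

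The cost is one derived variable and a few lines of SAP text. No new data are needed, because mapping films to visit windows already requires their dates. The template code in SAP 5.4.3.2 takes the standardized slope as an input, so its model statement does not change.
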